#### DOCUMENT HISTORY

Document	Date of Issue	Overall Rationale
HVO-CS-008, V3.0	08 July 2021	The Protocol Amendment has been created to revise the below listed information. Infusion rate was amended to a stable rate of up to 2.0mL/min The incorrect timepoints in the SoA for randomisation and immune markers were amended from post- to pre-inoculation. Storage temperature of SAB-176/Placebo doses, which was inaccurate, was corrected. Additional information on blinding and randomisation process was added.
HVO-CS-008, V2.0	12 May 2021	Not applicable (first approved version).

#### PROTOCOL AMENDMENT SUMMARY OF CHANGES

#### Protocol Amendment 01

Section / Title	Description of Change	Brief Rationale
1.2. Schedule of Activities (SoA): Randomisation	Randomisation timepoint was changed from Post- inoculation to Pre- inoculation.	The change was made to allow enough time for preparation, QP release and delivery of doses to investigational site.
1.2. SoA: Blood -immune marker	Time point for the immune marker was corrected from Post inoculation to Pre- inoculation	Blood immune marker time point was incorrect in the previous protocol version.
6.1. Table 2: Study Intervention	Vial concentration of SAB- 176 was corrected in the Packing and Labeling section.	SAB-176 concentration from previous batch was left in the protocol by mistake and has been corrected.
6.2., 6.2.1. Interventional Product / Placebo	The infusion rate of interventional product was changed to a stable rate of up to 2.0mL/min.	Infusion rate was corrected based on the safety and tolerability profile of the Phase I study, with the highest administered dose of 50mg/kg. Dose level in this study is 25mg/kg.
6.2., 621. Interventional Product / Placebo	Storage temperature of SAB- 176 / Placebo doses was corrected from 2°C-8°C to 15°C-25°C. Additional wording was added for clarity.	Storage temperature range 2°C-8°C relating to SAB-176 vials (bulk supplies) was incorrect for SAB-176 / Placebo doses which must be stored at 15°C-25°C.

# 1. Protocol Synopsis

Phase	Phase 2a
Clinical Study Site	Single centre, hVIVO Services Limited
Indication	Treatment of influenza caused by Type A and Type B influenza viruses
Study Type	Interventional
Design	Up to 60 eligible participants will be randomized in a 1:1 ratio to receive either SAB-176 (up to 50 mg/kg dose) or placebo. Healthy adult participants will be pre-screened for serosuitability for Influenza A/California/2009 H1N1 challenge virus. Serosuitable participants who sign the study specific informed consent form (ICF) will be challenged with an intranasal administration of Influenza A/California/2009 H1N1 virus on Day 0. Participants will be given an intravenous (IV) infusion of SAB-176 or placebo on Day 1. Participants will be held in quarantine until Day 8.
Investigational Medicinal Product (IMP)	SAB-176 (a quadrivalent anti-seasonal influenza immunoglobulin product)
IMP dose	Single dose up to 50 mg/kg
Pharmaceutical form	Purified human immunoglobulin G (hlgG) in a sterile liquid formulated in 10 mM glutamic acid monosodium salt, 262 mM D-sorbitol, 0.05 mg/mL Tween 80, pH 5.5, administered as a liquid solution for injection in 0.9% sodium chloride (saline).
IMP route	Intravenous infusion
Control compound	Placebo
Randomisation	1:1 ratio active:placebo
Challenge virus	Influenza A/California/2009 H1N1 virus
Challenge virus route	Intranasal delivery
Challenge virus titre	Approximately $3.5 \times 10^6 \log_{10}$ tissue culture infectious dose (TCID 50 )
Study population	Healthy male and/or female participants, between 18 to 45 years of age, pre-screened for serosuitability for Influenza A/California/2009 H1N1 challenge virus i.e., have levels of influenza antibodies compatible with susceptibility to influenza infection.
Summary of study design	This is an exploratory randomised, Phase 2a, double blind, placebo-controlled study to evaluate the safety and treatment efficacy

	of SAB-176 against Influenza A/California/2009 H1N1 virus infection in healthy adult participants.	
	The study is divided into the following study phases:	
	Screening phase:	
	• Screening from 56 days (90 days for influenza serology) up to Day -3. Historical pre-screening data collected through the hVIVO Generic Screening process within 56 days (90 days for influenza serology) up to Day -3 may be transferred to this study after the study specific ICF has been signed by the participant.	
	Inpatient phase:	
	
 
Admission to the Quarantine Unit on Day -2 / -1; resident in the Quarantine Unit for approximately 11 days (e.g., from admission on Day -2 to planned discharge on Day 8).
 
Inoculation with Challenge virus on Day 0.
 
IV infusion with SAB-176 or placebo on Day 1.
 
Discharge from the Quarantine Unit planned on Day 8.
 
	
	Outpatient phase: follow-up visit:	
	• Day 28 (±3 days).	
Expected duration of participant participation	Approximately 5 weeks from signing study specific ICF to the participant's last scheduled visit.	
Overall duration of clinical phase	The length of the clinical phase is estimated to last approximately 15 weeks from first participant first visit to last participant last visit.	
End of study	The end of the study is defined as the date of the last scheduled visit of the last participant in the study.	
Procedures and assessments	
 
During the study, the following assessments and procedures will be performed:
 
Informed Consent
 
Eligibility Criteria
 
Medical & Medication History
 
Demographics
 
Height & Weight and Body Mass Index
 
Alcohol Breath Testing
 
Urine Sample Collection (safety, drugs of abuse, cotinine, pregnancy)
 
Complete Physical Examination
 
Directed Physical Examination
 
Vital Signs
 
Tympanic Temperature
 
Electrocardiogram
 
Spirometry
 
Symptom Diary Cards 
 
Visual Analogue Scale
 
Patient Health Questionnaire (PHQ-9)
 
 
 
	

	
 
Generalised Anxiety Disorder Questionnaire (GAD-7)
 
Wearable, if applicable
 
Inoculation with Challenge virus
 
IV Infusion SAB-176 or placebo
 
Nasal Discharge Collection
 
Blood Sample Collection
 
Nasal Sample Collection
 
Adverse events (AEs) and Concomitant Medications.
 

Sample size	Up to 60 participants will be inoculated with the Challenge virus. Note : A participant will be considered 'enrolled' into the study once he/she has signed the study specific ICF and eligibility is confirmed and has been inoculated with the Challenge virus. Potential participants who are screened under hVIVO generic screening process for the purpose of determining suitability for the study, but do not sign the study specific ICF to participate in the study, are not considered enrolled.
Replacement policy	If a participant discontinues from study intervention OR withdraws from the study a replacement participant may be enrolled if deemed appropriate by the Investigator and Sponsor. The replacement participant will generally receive the same allocated blinded study intervention as the participant being replaced. The replacement participant will be assigned a new unique randomization number.
	Sample size justification
	Up to 60 participants will be inoculated with the Challenge virus. The statistical powering selected for this study is estimated to be sufficient for the primary objective and based upon only the primary endpoint. The targeted power for this study's endpoint is for 80% using a two-sided type-one error rate of 5%. The sample size of 60 participants (30 in each arm) will allow detecting a 60% relative reduction in the quantitative reverse transcriptase-polymerase chain reaction (qRT-PCR) area under the curve (AUC) virology with SAB-176 assuming an 81% coefficient of variation in the control arm.
Statistics	The PCR-AUC data is based on log-transformed PCR data.
	The sample size indicates the number of participants to be inoculated with the Challenge virus.
	Primary efficacy analysis
	The main estimator of the primary endpoint (the median area under the viral load-time curve [VL-AUC] of Influenza A/California/2009 H1N1 virus as determined by qRT-PCR on nasal samples [virology]), will be analysed on the Per Protocol (PP) Analyses Set.
	The calculation of the VL-AUC will be performed on log 10 -transformed PCR data using the trapezoidal summation rule based on actual time intervals in hours.

Descriptive statistics and the 95% confidence interval (CI) will be presented by treatment group. The difference between the two group will be analysed using the Wilcoxon rank sum test. The two-side p-value will be presented.						
Objectives		Endpoints				
	Priı	nary				

 
To evaluate the effect of reducing influenza viral le when compared to placebox
 
	oad qRT-PCR	
 
Area under the viral load-time curve (VL-AUC) of Influenza A/California/2009 H1N1 virus, as determined by qRT-PCR on nasal samples.
 
				
Secondary						

 
To further evaluate the effering reducing viral loads / vir qRT-PCR due to A/California/2009 H1N1 virus
 
	al shedding in Influenza	
 
Peak viral load as defined by the maximum viral load determined by quantifiable qRT-PCR measurements.
 
Duration of influenza quantifiable qRT-PCR
 
				
placebo.		measurements.				
To evaluate the effect of reducing viral loads / viral s culture due to Influenza A/e	hedding in cell	
 
VL-AUC of Influenza A/California/2009 H1N1 virus, as determined by cell culture measurements.
 
				
H1N1 virus, compared to pla	acebo.	• Peak viral load as defined by the maximum viral load determined by quantifiable cell culture measurements.				
		Duration of influenza quantifiable cell culture measurements.				

 
To evaluate the effect of reducing symptoms due A/California/2009 H1N1 virus placebo.
 
	to Influenza	• Area under the curve over time of total clinical symptoms score (TSS-AUC) as measured by graded symptom scoring system (categorical and visual analogue scales).				
		• Peak symptom diary card score: peak total clinical symptoms (TSS) as measured by graded symptom scoring system (categorical and visual analogue scales).				
		• Peak daily symptom score: Individual maximum daily sum of symptom score.				
		• Number (%) of participants with Grade 2 or higher symptoms.				

	Objectives	Endpoints
•	To evaluate the effect of SAB-176, in reducing the incidence of symptomatic infection due to Influenza A/California/2009 H1N1 virus, compared to placebo.	
 
RT-PCR-confirmed symptomatic influenza infection defined as:         
 
RT-PCR-confirmed influenza infection, AND
 
Clinical symptoms.
 
 
 
Culture lab-confirmed reduction of symptomatic influenza infection defined as:         
 
Lab-confirmed culturable influenza infection, AND
 
Clinical symptoms.
 
 
 

•	To evaluate the safety of SAB-176, when compared to placebo.	
 
Occurrence of unsolicited adverse events (AEs) from IV infusion up to Day 28 follow-up.
 
Occurrence of serious adverse events (SAEs) from IV infusion up to Day 28 follow- up.
 

•	To evaluate the safety of the Influenza A/California/2009 H1N1 virus challenge model.	
 
Occurrence of unsolicited AEs related to the viral challenge from viral challenge (Day 0) up to Day 28 follow-up.
 
Occurrence of SAEs related to the viral challenge from viral challenge (Day 0) up to Day 28 follow-up.
 
Use of concomitant medications from viral challenge (Day 0) up to Day 28 follow up.
 

	Tertiary/Exploratory*	
•	To further explore the effect of SAB-176, in reducing the incidence of influenza illness due to Influenza A/California/2009 H1N1 virus, compared to placebo.	
 
Upper Respiratory Tract illness,
 
Lower Respiratory Tract illness,
 
Systemic Illness,
 
Febrile Illness,
 
Mild to moderate symptoms.
 

•	To explore the Minimal Clinically Important Difference (MCID) in instrument change (e.g., symptom diary cards).	
 
The average amount of instrument-assessed change for all participants who rate themselves as "a little better" or "somewhat better.
 
Additional endpoints may be considered for this objective and added at a later stage.
 

[figure not shown]

Objectives	Endpoints

 
To explore the effect of SAB-176, i reducing the incidence of infection due t Influenza A/California/2009 H1N1 virus compared to placebo.
 
	respiratory samples by qRT-PCR and cell
To further explore the safety of th Influenza A/California/2009 H1N1 viru challenge model.	

 
To explore the utility of wearabl continuous monitoring for assessin Influenza A/California/2009 H1N1 viru infection/disease.
 
	monitoring may be explored in relation to
To explore genomic, transcriptomic, an immunological markers of Influenza A/California/2009 H1N1 viru infection, as well as the effect of SAB-176	f investigated to assess i) the host baseline status, ii) response to infection, and
	
 
Ribonucleic acid (RNA) transcriptomics (e.g., RNA sequencing, microarray)
 
This is a non-exhaustive list.
 

\*Note that tertiary objectives and endpoints are optional and might be assessed only if needed; therefore, not all tests might be performed and reported.

## 1.1. Study Schematic: On-study Participant Progression

\*NOTE: Release from quarantine is foreseen at Day 8 (8 days post-inoculation) in case no virus is detected by qualitative virus antigen test or polymerase chain reaction (PCR) (negative virus antigen test or PCR below Ct cut-off) and the participant has no clinically significant symptoms. If the participant continues to have clinically significant symptoms and/or detectable virus on Day 8, additional extended quarantine stay may be required at the discretion of the Investigator.

# hvivo

# 1.2. Schedule of Activities (SoA)

	Screening					(	QUARANT	TINE ISC	LATION	1							Early
Study phase →	phase*	Admission to Human viral challenge (HVC)							Post	HVC da	iys		Discharge	Clinic visit		withdrawal visit	
Study day 🗲	Day -56 (Day -90 for	Day	Day		Day 0		Day	Day	Day	Day	Day	Day	Day	Day	Follow-up		
Procedure V	influenza serology) to Day -3	-2	-1	Pre	Challenge	Post	1	2	3	4	5	6	7	8	Day 28 (± 3 days)		
Written consent (a)	х	X	(°														
Eligibility criteria (b)	Х	X	(°	Х													
Medical & medication history, and changes	х	×	(°														
Demographics	Х																
Height & weight, and body mass index (BMI) (c)	Х	×	(°											(X)	(X)		(X)
Alcohol breath test	Х	X	(°												Х		Х
Urinalysis	Х	X	(°											Х	Х		Х
Urine drugs of abuse	х	X	(°												Х		Х
Urinary cotinine test	Х	X	(°														
Urine pregnancy test (d)	Х														Х		Х
Complete physical examination	Х	×	(°											х	х		х
Directed physical examination (incl. nasal)				х		х	Xq	х	х	х	Х	х	х				
Vital signs (heart rate [HR], respiratory rate [RR], blood pressure [BP] systolic BP and diastolic BP, peripheral arterial oxygen saturation [SpO 2 ]) (e)	Х	X°	TDS		TDS		8X	TDS	TDS	TDS	TDS	TDS	TDS	х	x		x
Tympanic temperature	х	X°	TDS		TDS		TDSq	TDS	TDS	TDS	TDS	TDS	TDS	Х	X		Х
Symptom diary card		X°	TDS		TDS		TDSq	TDS	TDS	TDS	TDS	TDS	TDS	Х			
24-hour tissue count and nasal discharge (f)			Х		х		х	х	х	Х	Х	х	х	х			(X)
12-lead electrocardiogram (ECG)	Х	×	(°				Xr		х				х		х		х
Spirometry (g)	Х	X	(°						Х				Х		X		Х

	Screening					(	QUARAN	TINE ISC		N						Early
Study phase 🗲	phase*	Admission to quarantine (HVC) Post HVC days Discharge							Clinic visit	withdrawal visit						
Study day →	Day -56 (Day -90 for	Day	Day		Day 0		Day	Day	Day	Day	Day	Day	Day	Day	Follow-up	-
Procedure V	influenza serology) to Day -3	-2	-1	Pre	Challenge	Post	1	2	3	4	5	6	7	8	Day 28 (± 3 days)	
Patient Health Questionnaire (PHQ-9)	X	)	۲°													
Generalised Anxiety Disorder Questionnaire (GAD-7)	х	>	۲°													
Wearable (continuous monitoring e.g., vital signs, temperature, ECG), if applicable		•					contin	uous s								x
Product Administration																
Challenge virus inoculation					Х											
Randomisation				Х		X										
Investigational medicinal product (IMP) / placebo dosing							х									
Collection of Blood Samples																
Serum follicle stimulating hormone (FSH) (h)	х															
Serum beta-human chorionic gonadotrophin (β-HCG) pregnancy test (i)		>	۲°													(X)
Human immunodeficiency virus (HIV), Hepatitis A, B, and C tests	х															
Haematology (j)	Х	>	۲°				Xd		Х				Х	(X)	Х	X
Biochemistry (j)	х	>	۲°						Х				Х	(X)	Х	Х
Coagulation (j)	Х	>	( °				Xd		Х				Х	(X)		Х
Cardiac enzymes	х	)	۲°						х	1			Х			
Thyroid function test	х	()	<)°									1				
Blood - immune markers (k)	Х	X°	X	х			Xq	х	х	х	Х	Х	Х	х	Х	Х
Blood – transcriptomics markers			BD	х		х	BDq	BD	BD	BD	BD	BD	BD	х		

	Screening		QUARANTINE ISOLATION									Γ	Early				
Study phase >	phase*	Admission to quarantine		Human viral challenge (HVC)					Post	HVC da	iys	Discharge	Clinic visit		withdrawal visit		
Study day →	Day -56 (Day -90 for	Day	Day		Day 0		Day	Day	Day	Day	Day	Day	Day	Day	Follow-up		
Procedure V	influenza serology) to Day -3	-2	-1	Pre	Challenge	Post	1	2	3	4	5	6	7	8	Day 28 (± 3 days)		
Blood – deoxyribonucleic acid (DNA) - genomics		>	۲°														
Blood - Pharmacokinetics (PK)		>	۲°				2X t	Х		Х		Х		Х	Х		Х
Blood - anti-drug antibodies (ADA)		>	۲°				2X t	х		Х		х		х	х		х
Collection of Respiratory Samples																	
Nasopharyngeal swab / nasal wash - Respiratory pathogen screen (I)	т	X°	(X) p														
Nasopharyngeal swab / nasal wash - Rapid viral antigen test or polymerase chain reaction (PCR)														(X) p			(X)
Nasopharyngeal swab / nasal wash – Virology (m) and exploratory research	т		x				BDq	BD	BD	BD	BD	BD	BD	х			х
Nasal sample (nasosorption / mid turbinate swab) – PK and exploratory immunology			х				Xď	x	Х	х	х	х	х	х			
Safety Assessments																	
Adverse events (n)	х		continuous							Х							
Concomitant medications (n)	Х							con	tinuous								Х

#### KEY NOTES FOR SCHEDULE OF EVENTS

Х	Once
BD	Twice Daily. The timing of the baseline assessment will be the guide to establish the windows for subsequent measurements. For scheduling purposes, the baseline assessment will be defined as the first day when BD measurements are performed. Subsequent sampling / measures will be performed at the same time ±1 hour.
TDS	Three Times Daily. The timing of the baseline assessment will be the guide to establish the windows for subsequent measurements. For scheduling purposes, the baseline assessment will be defined as the first day when TDS measurements are performed. Subsequent sampling / measures will be performed at the same time ±1 hour
Т	To determine tolerance of the procedure only (sample will not be tested).
*	All screening assessments will be performed under hVIVO Generic Screening process. Historical pre-screening data collected through the hVIVO Generic Screening process within 56 days (90 days for influenza serology) up to Day -3 may be transferred to this study after the study specific ICF has been signed by the participant.

# hvivo

CONFIDENTIAL

а	Study specific consent may occur on the day of admission, providing all required eligibility information has been collected through hVIVO Generic Screening process.
b	Only the applicable Inclusion / Exclusion criteria will be reviewed at each time point.
с	Height will be taken at Screening only.
d	Urine pregnancy tests will be performed in female participants of childbearing potential.
е	Vital signs will be taken at the same time(s) each day (±1 hour). On Day 1 the vital signs will be performed pre-infusion, and at 15 minutes, 30 minutes, 60 minutes, 90 minutes, 2 hours, 4 hours, and 8 hours after the start of the drug infusion.
f	Distribution of paper tissues and bags will start on Day -1, with the first collection on Day 0. Thereafter collection of tissues will occur at the same time points (±1 hour) with tissues distributed 24 hours ahead.
g	Assessments will be performed at the same time points (±1 hour) during quarantine.
h	A serum FSH test will be performed in all post-menopausal female participants.
i	Blood serum pregnancy test (β-hCG) will be performed in all female participants.
j	Blood may be drawn under non-fasted conditions. Repeat bloods may be drawn under fasted conditions if a lipid profile (triglyceride) or glucose is required (at Principal Investigators [PIs] discretion).
k	Blood will be collected for: i) virus serology (influenza antibody assay) to determine eligibility (at screening) and seroconversion (at Day -2 / -1 & Day 28), and ii) exploratory immune markers.
I	Nasopharyngeal swab or nasal wash for respiratory virus screen to assess for the presence of other respiratory viruses; if found positive the participant will not be eligible for the current quarantine.
m	Nasopharyngeal swabs (or nasal wash, if appropriate) will be collected for viral load assessments and exploratory immunology. Post inoculation nasal virology samples will be collected and used for qRT-PCR and viral culture assay.
n	Adverse events and concomitant mediations are reviewed throughout the study including pre- and post-infusion with IMP/placebo and pre- and post-inoculation.
0	Can be performed on Day -2 or Day -1. If admission at Day -1, all procedures scheduled for Day -2 can be performed on Day -1, as appropriate.
р	Optional and may be collected or not as per PI discretion for exploratory research.
q	Pre-infusion (only applicable to the first assessment on Day 1).
r	Post-dose ECG.
s	An exploratory wearable may be used to capture continuous measures parameters such as: HR, heart rate variability, SpO 2 , temperature, ECG. This may include a period of up to 4 weeks prior to quarantine admission and up to 4 weeks post discharge from quarantine.
t	PK and ADA samples to be taken on Day 1 (IMP / placebo administration day): one sample pre-infusion and one sample at 1-hour post-infusion end (infusion end includes any time required for flushing).
Notes:	Parenthesis indicates the assessment may be optional, or at the PI's discretion. For all participants TDS assessments will commence on Day 0, the first assessment will be pre-virus challenge. The PI may perform additional safety assessments as required. Where any nasal sampling time points occur together, the order of sampling will typically be (1) nasosorption, (2) nasopharyngeal swab followed by (3) nasal wash

GENOMIC, TRANSCRIPTOMIC AND PROTEOMIC SAMPLES									
	Yes 🛛 No								
Deoxyribonucleic acid (DNA) / ribonucleic acid (RNA) / proteomic sample collection:									
Consent considerations:	Genetic consent. Future use of remaining samples for exploratory research: blood samples (including processed blood) and respiratory samples for biomarker analysis relevant to the exploratory objectives of the study.								

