#### 2.3.1.1. Risks of SAB-176

SAB-176 is currently concluding a Phase 1 clinical trial (ClinicalTrials.gov identifier: NCT04471038). All participants have been infused with no serious adverse events (SAEs) reported through the highest dose cohort of 50 mg/kg and it appears to be safe and well tolerated. A previous Phase 1 study of SAB-301 (anti-Middle Eastern Respiratory Syndrome virus immunoglobulin) also derived from Tc bovines was shown to be safe and well tolerated at the highest dose of 50 mg/kg (ClinicalTrials.gov identifier: NCT02788188). It is anticipated that the risks for this Phase 2a study will be similar to the Phase 1 studies of SAB-176 and SAB-301 and the use of hIVIg with some unique considerations for proteins of animal origin as discussed below.

Based on hIVIg, common side effects may include:

- headache
- injection site reaction
- nausea
- urticaria
- fatigue
- arthralgia
- pyrexia.

Less common side effects may include:

- vomiting
- back pain
- rash.

Serious side effects seen with hIVIg that could be seen with SAB-176 include:

- Hyperproteinaemia, with resultant changes in serum viscosity and electrolyte imbalances may
  occur in patients receiving IVIg therapy (Steinberger et al. 2003). Humans routinely receive up to
  1 to 2 grams/kg of hIVIg to treat Guillain-Barre syndrome and other immune related neuropathies.
  Therefore, the addition of 50 mg/kg IgG as SAB-176 is a relatively small amount and is unlikely
  to cause AEs related to increased viscosity.
- Aseptic Meningitis Syndrome has been reported with IVIg treatments, especially with high doses or rapid infusion. This risk is anticipated to be minimized given the low amount of protein and relatively slow infusion.
- Haemolysis, either intravascular or due to enhanced red blood cell (RBC) sequestration, can be seen with human IVIg. This risk is anticipated to be low given the lack of exposure of the cows to human RBC antigens.
- Volume overload has been reported with human IVIg. This risk is anticipated to be minimized given the low amount of protein and small total volumes administered.

There may be additional risks of SAB-176 given its animal origin. SAB-176 is a fully human IgG so it is anticipated the risk would be less, though there may be residual animal proteins. The most similar product would be Horse Heptavalent Botulism Antitoxin which is an equine derived non-human polyclonal IgG polyclonal:

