(http://www.fda.gov/downloads/BiologicsBloodVaccines/BloodBloodProducts/ApprovedProducts/Licensed ProductsBLAs/FractionatedPlasmaProducts/UCM345147.pdf),

There is the risk of off-target binding of the IVIg. In the worst case, this could cause immune activation (cytokine storm). The tissue cross reactivity assays do not predict any off-target binding, and this has not been seen in any other animal IVIg (of antigen-binding fragment [Fab]) preparations, so this risk is considered low.

For Horse Heptavalent Botulism Antitoxin, the most common adverse reactions (ARs) in all healthy participants were headache (9%), pruritus (5%), nausea (5%), and urticaria (5%). Other ARs reported in less than 4% of participants included pyrexia and throat discomfort. All reported ARs were considered mild or moderate. No serious ARs were reported. Two moderate acute allergic reactions that required premature termination of the infusion and treatment were reported. Reactions were predefined as mild if the participant was aware but could tolerate the symptoms. Moderate reactions were predefined as discomfort enough to interfere with normal daily activity.

The development of antibodies to bovine proteins and potential for food allergies is a theoretical concern. There is precedent for animal antibodies (or Fabs) being obtained from animal plasma and given to humans.

- Rabbit Anti-thymocyte Globulin [Thymoglobulin] (http://products.sanofi.ca/en/thymoglobulin.pdf).
- Horse Anti-thymocyte Globulin [Atgam] (http://www.fda.gov/downloads/BiologicsBloodVaccines/BloodBloodProducts/ApprovedProducts /LicensedProductsBLAs/FractionatedPlasmaProducts/UCM199603.pdf).
- Horse Heptavalent Botulism Antitoxin
   (http://www.fda.gov/downloads/BiologicsBloodVaccines/BloodBloodProducts/ApprovedProducts
   /LicensedProductsBLAs/FractionatedPlasmaProducts/UCM345147.pdf).
- Sheep Digoxin Immune Fab [DigiFab] (http://www.fda.gov/downloads/BiologicsBloodVaccines/BloodBloodProducts/ApprovedProducts /LicensedProductsBLAs/FractionatedPlasmaProducts/ucm117626.pdf).
- Sheep Digoxin Immune Fab [DigiBind] (http://dailymed.nlm.nih.gov/dailymed/archives/fdaDrugInfo.cfm?archiveid=19044).
- Sheep Crotalidae Polyvalent Immune Fab [CroFab] (http://www.crofab.com/documents/CroFab-Prescribing\_Information.pdf).

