# 8.9. Tympanic Temperature

The study specific normal range for tympanic temperature is detailed in Appendix 4. The severity of out of normal range values will be assigned using the DMID toxicity scale as a guide.

Temperature may be more frequently monitored in quarantine if appropriate.

Following viral challenge, pyrexia will be expected and presumed to represent virus infection consequent to viral challenge and will not be additionally captured as an AE unless it meets the definition of an AE and is deemed to be clinically significant (in the opinion of the Investigator) to be classed as an AE.

Following viral challenge all unexpected (in the opinion of the Investigator) pyrexia will be captured as an AE, along with all other occurrences that meet the criteria for an AE.

Febrile illness is defined as any occurrence of temperature ≥37.9°C.

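### Day 1 temperature is not read at the infusion-timed vital-sign checks, so a brief post-infusion fever can go unrecorded and the onset of a longer one is poorly timed

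*Combined protocol and SAP*

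**What the plan says.** In section 1.2 (Schedule of Activities) the timed set is defined as "Vital signs (heart rate [HR], respiratory rate [RR], blood pressure [BP] systolic BP and diastolic BP, peripheral arterial oxygen saturation". Section 8.8 lists the same four measures. Footnote e fixes the Day 1 times: "On Day 1 the vital signs will be performed pre-infusion, and at 15 minutes, 30 minutes, 60 minutes, 90 minutes, 2 hours", followed by 4 and 8 hours after the start of infusion.

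Tympanic temperature has its own row, three times daily (TDS) on Day 1 with note q, which reads "Pre-infusion (only applicable to the first assessment on Day 1". The other two readings follow the general TDS rule: "Subsequent sampling / measures will be performed at the same time ±1 hour". The documents do not state the clock times or the gap between TDS readings.

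Two other sections bear on the point:

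- Section 2.3.1.1 introduces a list that includes pyrexia with "Based on hIVIg, common side effects may include".
- Section 8.9 says that after challenge "pyrexia will be expected and presumed to represent virus infection consequent to viral challenge". Such fever becomes an adverse event only if the investigator judges it clinically significant or unexpected. The same section allows extra readings: "Temperature may be more frequently monitored in quarantine if appropriate".

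**The concern.** Safety of SAB-176 against placebo from infusion onwards is a secondary objective, and fever is an effect that the protocol itself anticipates by analogy with human immunoglobulin. Infusion takes place the day after inoculation, and fever from then on is presumed viral. Timing relative to the infusion is one of the few pieces of information that could help the investigator separate the two, and section 10.3.6.5 asks for the temporal relationship to be considered when causality is assessed. Yet temperature is the one bedside measure with no required reading at a set time after infusion start.

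Two things are lost. A short fever without symptoms may leave no scheduled record. A longer fever may be recorded with an onset known only to within several hours.

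**Working it through.** **Counting the required readings (documents only).** Footnote e gives pre-infusion + 15, 30, 60 and 90 min + 2, 4 and 8 h = 8 readings, which matches the 8X in the Schedule of Activities. Seven of these come after infusion start, five of them within 2 h. Temperature has 3 readings on Day 1, less 1 pre-infusion = 2 later readings, neither tied to the infusion.

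**Precision of onset.** Scheduled temperature readings bracket onset to one TDS gap (assumed 4-8 h; the ±1 h windows could add up to 2 h). At the footnote e times the intervals are 15, 15, 30, 30 and 30 min up to 2 h, then 2 h and 4 h.

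**Chance that a scheduled reading falls within a fever (illustration).** None of these inputs is in the documents: TDS gap g = 4, 6 or 8 h; fever lasting d hours; onset uniform over 0 to W hours after infusion start; infusion starting at a uniformly random time between the first and second readings.

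- Current plan: detection = min(1, d/g). For d = 1: 1/4 = 25%, 1/6 = 17%, 1/8 = 13%. For d = 2: 50%, 33%, 25%. For d = 4: 100%, 67%, 50%.
- With the added readings: detection = 1 − m(1 − d/g), where m is the share of the onset window from which no added reading is reached. For d = 1, m = 0 when W = 2. When W = 4, m = 1/4 (onset between 2 and 3 h). When W = 8, m = 4/8 (onset between 2 and 3 h or between 4 and 7 h).

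| 1 h fever, onset window | Current, g = 4 / 6 / 8 h | With added readings |
|---|---|---|
| 0-2 h | 25 / 17 / 13% | 100 / 100 / 100% |
| 0-4 h | 25 / 17 / 13% | 81 / 79 / 78% |
| 0-8 h | 23 / 17 / 13% | 63 / 58 / 56% |

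For example, W = 4 and g = 4 gives 1 − 0.25 × 0.75 = 0.81, and W = 8 and g = 8 gives 1 − 0.5 × 0.875 = 0.56. The 23% is below 25% because a late onset can come after the day's third reading. A simulation agrees with the table. For a 2 h fever the added readings give 100% for W = 2 or 4, and 88 / 83 / 81% for W = 8.

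Note q does not say how long before infusion the first reading is taken. If infusion starts within 1 h of it (an assumption), current detection of a 1 h fever is 0% for onset within 2 h, and 0-25% for onset over 0-4 h.

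**What 30 per arm can show.** Two-sided Fisher tests:

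- 5/30 v 0/30: 2 × C(30,5)/C(60,5) = 0.052.
- 6/30 v 0/30: 2 × C(30,6)/C(60,6) = 0.024.

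Six fevers against none are therefore needed for p < 0.05. Power is P(X ≥ 6), with X binomial on 30: 7% for a true 10% v 0%, and 57% for 20% v 0%. For the equine antitoxin, section 2.3.1.1 says "Other ARs reported in less than 4% of participants included pyrexia and throat discomfort"; at 4% the expected count is 30 × 0.04 = 1.2.

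**Interaction with the illness definitions.** Section 10.6.2 applies from Day 1, defines febrile illness as any temperature of at least 37.9°C confirmed by a repeat 20 to 60 min later, and lets febrile illness qualify as systemic illness. The 30, 60, 90 and 120 min readings are 30 min apart, so two consecutive ones could meet the confirmed definition by themselves. Scheduled readings over Days 1-8 would rise from 3 × 7 + 1 = 22 to 29.

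**The case against.** The case for leaving the plan alone is that existing cover is broad:

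- Staff are present at seven checks after infusion start.
- Adverse event review is continuous and records onset time and causality.
- Section 8.9 and the schedule notes allow extra readings.
- The TDS diary grades chilliness/feverishness in both arms, independently of the adverse event judgement.
- TDS temperature is itself recorded in both arms whatever the attribution.
- An opt-in wearable may record temperature continuously.

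The risk premise is also thin. The pyrexia listing is extrapolated from human immunoglobulin, which section 2.3.1.1 says is routinely given at up to 1 to 2 g/kg, against at most 50 mg/kg here (20 to 40 times less). Any Phase 1 temperature data would be in the Investigator's Brochure, which is not part of these documents.

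Most of this stands, and it is why the weight is low. What it does not supply is a required temperature at a known time after infusion start. The extra readings are discretionary, the diary cannot show a symptomless fever, and the wearable is optional.

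A reader might think temperature is already covered, because Appendix 4 lists it in its vital signs table. That table gives normal ranges, not a schedule; the schedule row and section 8.8 both define the timed set without it.

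A reader might also infer a participant-safety failure or a biased comparison of the arms. The documents support neither: monitoring around the infusion is close, and both arms follow the same schedule.

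**Conclusion.** The gap is real and exact in structure: seven required post-start readings for the other vital signs, against two for temperature, neither timed from the infusion. Its consequence is modest. It concerns brief fever that prompts no check, and the timing of any fever relative to dosing.

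The detection percentages illustrate and do not measure, since TDS gap, onset window and duration are all assumed. Fevers of 4 h or more are often caught already (50-100% under the 0-2 h and 0-4 h onset assumptions). It would be tempting to say that the added readings catch every fever; that holds in the 1 h illustration only for onset within 2 h of infusion start. Nor would they be expected to establish a product effect with 30 per arm. Their value is a descriptive temperature course by arm and better information for causality assessment. The primary endpoint is not affected. This is a cheap improvement at the low end of minor.

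**What to change.** Amend the Day 1 cell of the tympanic temperature row and footnote e so that temperature is also recorded at 15, 30, 60 and 90 min and at 2, 4 and 8 h after infusion start. Summarise these readings by arm and time point, descriptively and without a test.

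In sections 8.9 and 10.6.2, state that only these added infusion-timed Day 1 readings, and repeats prompted by them, are excluded from the exploratory febrile and systemic illness endpoints. All other readings should count as they do now, including the single Day 8 reading and any discretionary or symptom-prompted reading. Limiting those endpoints to TDS readings would be too narrow, because it would drop both of these.

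The cost is seven short ear readings per participant at checks that staff already attend (7 × 60 = 420 in all), some repeats, the CRF fields and the wording changes. Some early viral fevers will be picked up in both arms; the placebo arm is the comparator for these.
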